5.6 Multiple Comparison/Multiplicity

Since no formal statistical tests are planned for the primary and secondary analysis except for the subgroup analysis for this study, there are no provisions for multiple comparisons or multiplicity adjustment of study endpoints.

5.7 Interim Analysis and Data Monitoring

Interim analyses will not be conducted for this study.

5.8 Multicenter Studies

Given that the principal efficacy measure, MBL, is computed across the combined data across all participating sites, no by-site evaluation or statistical adjustment for site-to-site variation is planned. Summary presentations by site may be considered for specific descriptive variables, e.g., demographic factors, on a by-site basis if warranted. Site-specific data set information may also be prepared per regulatory inspection.

5.9 Subgroup Analysis

Descriptive summaries of absolute change in the median MBL from baseline to End-of-study will be provided for the following subgroups with no formal statistical testing;

- Age groups 18 to ≤ 35 and ≥ 36 years of age
- Race/Ethnicity
- BMI < 25 , 25 to < 30 , or ≥ 30

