4.2 Inclusion Criteria

1. Signed informed consent
2. Reports subjectively heavy menses for most menses when not using hormonal contraception or a copper IUD
3. Healthy females 18-50 years old, inclusive, at the time of enrollment
4. Able to read and write, as determined by study personnel
5. FSH value ≤ 30 mIU/mL at screening
6. Typical menstrual cycle length of 21-35 days with variation from cycle to cycle of typically 5 days or less

7. Has withdrawal bleeding in 2 of the 3 cycles during the Screening Phase with ≥ 80 mL per cycle as measured by the AH method
8. Uterine sound depth of ≥ 5.5 cm
9. Willing to comply with study visit schedule and assessments, including sanitary product collection and diary completion requirements
10. Documented (i.e., printed report) Pap testing, regardless of subject's age, and any indicated evaluation/treatment that demonstrates no need for further evaluation during the course of study participation (i.e., within 10 months after consent)
11. Planning to reside within a reasonable driving distance of a research site (approximately 150 miles) for duration of study participation
12. Willing to use a medication other than a NSAID as first-line treatment for any pain condition during the duration of study participation
13. Willing to abstain from heterosexual intercourse or use acceptable contraception during the screening phase; acceptable contraception includes male or female permanent contraception, withdrawal (if has been using as current method prior to screening) or a barrier method
14. If previously pregnant, at least one subjectively heavy menses prior to screening

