5.4 Standard Calculations

Variables requiring calculation will be derived using the following formulas:

- **Study day** – For a given date (*date*) on or after successful IUS insertion (*iusindt*), study day is calculated as:

$$\text{Study day} = \text{date} - \text{iusindt} + 1$$

For a given date (*date*) prior to successful IUS insertion (*iusindt*) or for subjects with failed insertion, study day is calculated as:

$$\text{Study day} = \text{date} - \text{iusindt}.$$

The day of successful IUS insertion is Study Day 1 and the day prior to IUS insertion is Study Day -1. There is no Study Day 0

Months – A duration expressed in months is calculated as the number of completed calendar months plus the proportion of any partial month completed. A month is calculated using the following formula: Duration in months = $(\text{date2}-\text{date1})/30.4$

- **Years** - A duration expressed in years between one date (*date1*) and another later date (*date2*) is calculated using the formula noted below:

$$\text{Duration in years} = (\text{date2}-\text{date1})/365.25$$

- **Age** - Age is calculated as the number of years from the date of birth (*DOB*) to the IUS insertion attempt date (*iusindt*). For displaying a subject's age, the following formula is used:

$$\text{Age (years)} = \text{floor}(\text{insertion attempt date} - \text{birthdate})/365.25$$

- **Body Mass Index (BMI)** - BMI is calculated using height (in cm) and weight (in kg) at Screening Visit 1:

$$\text{BMI (kg/m}^2\text{)} = \text{weight (kg)} / [\text{height (cm)} / 100]^2$$

- **Cycles of Use** – Cycles are calculated using the date the IUS was expelled/removed (from the IUS Discontinuation CRF). Total use duration expressed as the number of 28-day cycles is defined as IUS expulsion/removal date or date of Visit 8 - date of

IUS insertion ($i_{usindt}+1)/28$. If re-insertion for expulsion takes place, the last IUS expulsion/removal date or date of Visit 8 is used. If the expulsion/removal date is unknown then:

- Subjects who are still on treatment will have their last known date of product use used in the cycle calculations in lieu of an IUS expulsion/removal date or date of Visit 8, derived as follows: The last known date of product use will be the last date of on-study contact with the subject where she reported that the IUS is still in place

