9.3 Key Secondary Efficacy Variables

All key secondary outcomes will be summarized by descriptive statistics using the MITT Population except that the bleeding and/or spotting analyses will be summarized using both Safety and MITT Populations. The subgroup analysis of absolute change in the median MBL from baseline to End-of-study will assess differences for age, race/ethnicity, and BMI subgroups, no formal statistical testing will be performed.

Menstrual Blood Loss:

- Absolute change in baseline MBL to mid-treatment MBL (Cycle 3)
- Percent change from baseline MBL to mid-treatment MBL (Cycle 3)
- Absolute change from baseline to end of treatment (Cycle 6), including subgroup analysis for age, race/ethnicity, and BMI

- Percent change from baseline MBL to end of treatment MBL (Cycle 6)

Vaginal Bleeding Flow:

- Vaginal bleeding flow (none, spotting, and light, normal, or heavy flow [bleeding]) will be summarized based on the daily diary by incidence and duration of bleeding at each Cycle. Vaginal bleeding is recorded on the daily diary during the Screening Phase and baseline will be considered the cycle with the worst flow severity during the screening cycles.
 - Based on World Health Organization (WHO) terminology, bleeding and spotting are defined as:
 - Bleeding: any bloody vaginal discharge for which protection, such as pads is used
 - Spotting: any bloody vaginal discharge for which protection is not used; if spotting and bleeding occur on the same day, it is recorded as a bleeding day
 - Incidence of bleeding by 28-day cycle intervals post-insertion (none vs. spotting vs. bleeding; none vs. ≥ 1 day; 1-3, 4-7, >7, and >20 days; no bleeding vs. any bleeding) will be summarized
- Vaginal Bleeding Episodes
 - Based on the individual subject's daily diary of bleeding
 - A bleeding day is when sanitary protection is used
 - A bleeding episode is defined as light, normal or heavy bleeding during a minimum of one day as defined by a subject's subjective assessment
 - A bleeding-free day is defined as a day with either no bleeding or only spotting
 - A single bleeding episode will consist of all bleeding days separated by no more than one bleeding-free day. Separate bleeding episodes will consist of bleeding days separated by more than one bleeding-free day. An episode will be considered stopped with two consecutive bleeding-free days.

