10.2 Secondary Efficacy Outcomes

All secondary efficacy outcomes will be summarized by descriptive statistics using the MITT Population except that the bleeding and/or spotting analyses will be summarized using both Safety and MITT Populations. Additional summaries will be provided for the median MBL change from baseline to End-of-study for subgroups such as age (18 to ≤ 35 and ≥ 36 yo), race/ethnicity, and BMI (<25 , 25 to <30 , or ≥ 30).

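### The age formula as printed leaves 35-year-olds outside both age groups, and the subgroup summary of absolute MBL change can be confounded by baseline and is not uniquely defined

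*SAP*

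**What the plan says.** SAP 5.9 plans descriptive subgroup summaries without testing: "Descriptive summaries of absolute change in the median MBL from baseline to End-of-study will be provided". The age split is "Age groups 18 to ≤ 35 and ≥ 36 years of age". SAP 10.2 plans summaries of the "median MBL change from baseline to End-of-study for subgroups" for the same factors.

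In the outcome list of SAP 9.3, the subgroup clause is attached to one item only: "Absolute change from baseline to end of treatment (Cycle 6), including subgroup analysis for age, race/ethnicity, and BMI". Percent change to Cycle 6 is the next item and carries no subgroup clause. Neither SAP 9.2 nor SAP 10.1 plans the success proportion by subgroup. The opening paragraph of 9.3 says that the subgroup analysis is meant to look at differences between the groups.

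On age, SAP 5.4 says: "Age is calculated as the number of years from the date of birth" to the insertion attempt date. It then prints a formula for display in which floor encloses only the difference of the two dates, and the division by 365.25 stands outside. Eligibility (Protocol 4.2) is: "Healthy females 18-50 years old, inclusive, at the time of enrollment".

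**The concern.** **Age.** A difference of two dates is already a whole number of days, so floor does nothing to it and the quotient keeps its decimals. The two age groups leave the interval between 35 and 36 uncovered. A program that follows the SAP literally leaves those women out of the age table.

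**Measure.** For each woman, absolute change is baseline MBL multiplied by her proportional reduction. If the groups differ in baseline, the table can show a difference where the treatment works equally well, or can hide or reverse a real one. The trial itself defines success partly in relative terms (no more than 50% of baseline).

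**Definition.** SAP 5.9 and the opening of 9.3 describe a change in the median, which is a difference of two medians. SAP 10.2 describes a median change, which is the median of within-woman differences. SAP 5.9, 10.2 and the opening of 9.3 say End-of-study, which SAP 5.3.3 fills from Cycle 3 when Cycle 6 is missing or invalid. The 9.3 outcome list says Cycle 6. Two programmers could build different tables from the same plan.

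**Working it through.** SAP 5.9 states no figure, so there is none to reproduce.

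**1. Age**

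Inputs: the printed formula (SAP 5.4), the age groups (SAP 5.9) and the age range 18-50 (Protocol 4.2).

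Printed: floor(days)/365.25. Probably intended: floor(days/365.25).

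| Days from birth to insertion attempt | Printed age | Group | Completed years | Group |
|---|---|---|---|---|
| 12,783 | 34.998 | ≤35 | 34 | ≤35 |
| 12,784 | 35.0007 | none | 35 | ≤35 |
| 12,997 | 35.58 | none | 35 | ≤35 |
| 13,148 | 35.997 | none | 35 | ≤35 |
| 13,149 | 36.000 | ≥36 | 36 | ≥36 |

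The row of 12,997 days is a woman born 15 June 1984 with an insertion attempt on 15 January 2020.

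Birth dates covering ages 18-50 were enumerated against insertion dates from October 2018 to December 2020, every 15 days. Of 20,099 combinations at age 35, the printed formula leaves 20,075 (99.9%) in neither group. The other 24 lie on or about the 35th birthday. With the bracket moved, all 20,099 fall in the younger group. No other age is affected.

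Share of women: 18-50 inclusive covers 33 whole-year ages, and 1/33 = 3.0%, or about 3 of 100 enrolled. This assumes uniform ages; the documents give no age distribution.

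**2. Absolute change and baseline**

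Absolute change = baseline × proportional reduction. The documents' six-month reductions are 71% (Protocol 1, for a 52 mg LNG IUS) and 79.0% (Protocol 7.1.1, for this product). Baselines by subgroup are not given, so those below are assumed.

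- Equal 79% reduction: 100 × 0.79 = 79 mL; 150 × 0.79 = 118.5 mL. The gap is 39.5 mL with the same proportional effect.
- Equal 71% reduction: 100 × 0.71 = 71 mL; 150 × 0.71 = 106.5 mL. The gap is 35.5 mL.
- Reversal: 100 mL with a 90% reduction falls by 90 mL; 150 mL with 75% falls by 112.5 mL. The weaker proportional response shows the larger fall.

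To see how far baseline drives the result by chance alone, subgroups of 28 and 42 women were simulated. Baselines were log-normal (median 110, 130 or 150 mL; log-SD 0.30, 0.45 or 0.60, respectively), truncated at 80 mL. The truncation is a simplification, because entry needs only two of three cycles at 80 mL. Percent reduction was independent of baseline, with a mean of 71% or 79% and an SD of 20 to 30 points. All of these inputs except the mean reductions are assumptions.

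| Subgroup statistic | r² with subgroup median baseline |
|---|---|
| Change in medians (wording of 5.9) | 0.36 to 0.85 |
| Median of within-woman changes (wording of 10.2) | 0.15 to 0.53 |
| Median within-woman percent change | 0.00 |

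**3. The two statistics differ**

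Take three women with baselines of 90, 100 and 200 mL and end values of 5, 60 and 20 mL. The change in medians is 100 - 20 = 80 mL. The individual falls are 85, 40 and 180 mL, with a median of 85 mL.

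**The case against.** **Age.** The intent is almost certainly completed years. Floor would be pointless on a whole number of days, and a cut at ≤35 and ≥36 makes sense only for whole years. A bracket may also have been lost in typesetting or conversion to text, since the cycles-of-use formula in the same section has odd brackets too. A reader might infer that women would vanish unnoticed. The documents do not support that: SAP 5.1 requires independent program validation and consistency checks within tables, and groups that do not add up to the total should be caught. What stands is that the printed rule, if followed, gives a wrong table.

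**Measure.** Absolute MBL change is a prespecified key secondary outcome, the subgroup output is descriptive, and no decision rests on it. A reader might infer that absolute change mainly mirrors baseline. The documents do not establish this. The high reduction of 94% in Protocol 1 is a one-year figure, while this trial ends at Cycle 6. At 71-79% the r² ranges from 0.15 to 0.85, on assumed baselines. What stands is that baseline can confound the comparison, and that percent change, already planned overall, avoids it when the proportional effect is the same.

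**Success by subgroup.** Adding it is not free of drawbacks. At n=20 and 80% success, the 95% half-width is 1.96 × √(0.8 × 0.2/20) = 17.5 points. Such intervals would often reach below 70% through small numbers alone.

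**Conclusion.** The point holds as a minor one in three parts.

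- **Age gap:** certain on the printed text, and probably a bracket slip. It concerns practically all women aged 35, about 3 of 100 under the uniform-age assumption.
- **Confounding by baseline:** real in principle, since absolute change scales with baseline. Its size is unknown, because it depends on the spread of baseline MBL and on how much percent reduction varies between women. The 39.5 mL gap illustrates the mechanism and does not predict this trial's data.
- **Definition:** two statistics and two endpoint labels are in use, and the text does not settle which applies.

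The primary success proportion, its confidence interval and the 70% criterion are untouched.

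**What to change.** - **SAP 5.4:** write Age = floor((insertion attempt date - birthdate)/365.25), and state that the age groups use completed years.
- **SAP 5.9, 9.3 and 10.2:** name one statistic, the median of within-woman changes, and one endpoint label, stating whether a Cycle 3 value carried forward counts.
- **Same sections:** add the median within-woman percent change and baseline MBL by subgroup, beside the absolute change.
- **Optional:** show the success proportion by subgroup descriptively, with a note that its intervals will be wide and are not to be read against the 70% criterion.

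The cost is SAP wording and a few table columns. No new data are needed.

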6. ANALYSIS POPULATIONS

The Safety population will include all subjects enrolled who underwent an IUS insertion attempt, regardless of outcome.

The following subject populations will be used for efficacy analyses:

- Modified-Intent-To-Treat (MITT): All subjects with qualifying baseline data at study entry for whom the IUS is successfully inserted and for whom there is at least one assessment of MBL during the Treatment Phase Cycle 3 or Cycle 6. All MBL values reported for both validated and unvalidated used feminine hygiene products will be included. This is the main population for the efficacy analyses.
- Supportive MITT: A supportive subset of the MITT population with baseline and post-baseline MBL data reported collected from only validated feminine hygiene products. This population is to demonstrate the robustness of the efficacy analyses.
- Per Protocol (PP): A subset of the MITT population that excludes subjects with major protocol deviations that are determined to have impact on the data of MBL assessment.

- Intent-to-Treat (ITT): All subjects with qualifying baseline data at study entry for whom the IUS is successfully inserted. This population is for evaluation of the sensitivity of results obtained from the MITT-based assessments. The baseline MBL will be carried forward (BOCF) for subjects who provide no Treatment Cycle 3 and no Treatment Cycle 6 data.
- Intent-to-Treat (ITT) Excluding Subjects LTFU and Subjects Who Withdraw Consent (WC) Without Study IUS Removal: All subjects with qualifying baseline data at study entry for whom the IUS is successfully inserted, excluding subjects who were LTFU or withdrew consent without study IUS removal and had no MBL assessment after baseline at Treatment Cycle 3 and Cycle 6. The baseline MBL will be carried forward (BOCF) for subjects who provide no Treatment Cycle 3 and no Treatment Cycle 6 data except for those subjects who were LTFU or withdrew consent without study IUS removal. This population is for evaluation of the sensitivity of results obtained from the MITT-based assessments.

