4. STUDY POPULATION SELECTION

4.1 Subject Selection

Approximately 100 subjects who qualify after screening will be enrolled in this study. Study entry (enrollment) is defined as the initiation of a study IUS insertion procedure. Subjects must fulfill all of the inclusion criteria and not meet any of the exclusion criteria to be eligible for enrollment.

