6.6 IUS Insertion Definitions

Up to two insertion attempts are permitted.

- An **insertion attempt** starts with placement of the IUS inserter through the external cervical os. IUS insertion ends with completion of cutting the IUS threads following successful intrauterine IUS placement or IUS insertion failure.
 - **IUS insertion failure** is considered to occur when after the IUS inserter passes through the external os of the cervix and completion of IUS insertion is not achieved.
 - **Successful IUS insertion** is considered as retention of the IUS in the uterus through cutting of the strings, unless removed for incorrect placement as determined by ultrasound or other means within the duration of the same clinic visit; the day of successful IUS insertion is considered Study Day 1.

- Note that **IUS insertion** is the general process that starts with opening of the LNG20 IUS kit with the intent to perform an insertion. The insertion process may stop before IUS insertion is attempted (see definition above); in such circumstances, an IUS insertion attempt has not occurred. Examples of procedure discontinuation prior to an insertion attempt include:
 - notable defect upon inspection of the product
 - loss of product sterility
 - inability to sound the uterus
 - subject intolerance of the procedure prior to LNG20 IUS contact with the external cervical os

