6.8 Treatment Phase Enrollment Visit (Visit 5)

The Treatment Phase Visit 5 should occur within 45 days of the screening visit (i.e., Visit 3 or Visit 4) that determined eligibility. An IUS insertion attempt enrolls the subject into the Treatment Phase. Second insertion attempts are allowed and can occur on the same day or different day, but a second attempt must be within 30 days of the first attempt. The day of successful IUS insertion is considered Study Day 1.

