7.1.16 Local Anesthesia

If the clinician uses cervical anesthesia during insertion or removal, there is an infrequent risk of the subject experiencing an unusual taste in her mouth, ringing in her ears, nausea or light-headedness. Rarely, a seizure or death can occur.

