7.13 Clarification of Adverse Events Related to Study Procedures

Any untoward event that occurs from the beginning of the IUS insertion procedure until completion of insertion, or from the beginning of the removal procedure until the completion of removal, will be reported as an AE. Bleeding and cramping/pain occurring during IUS insertion or removal will be recorded on the IUS Insertion and Removal CRFs, as appropriate. Any other insertion or removal AEs should be recorded on the AE CRF with a causality assessment of “related to IUS procedure.” If any AE meets the definition of a Serious Adverse Event, even if it is recorded on the diary or Insertion or Removal CRF, it should also be reported on the AE and SAE CRFs and submitted to Sponsor.

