9.2 Analysis Populations

The following subject populations will be created:

- Safety (Safety): All subjects enrolled who underwent the IUS insertion procedure, regardless of outcome.
- Modified-Intent-To-Treat (MITT): All subjects at study entry for whom the IUS is successfully placed in the uterus with valid baseline data and for whom there is at least one assessment of MBL during the treatment phase.
- Per Protocol (PP): A subset of the MITT population that excludes subjects with major protocol deviations (to be identified prior to data lock).

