11.5 Insertion

The number and percentage of subjects with a successful insertion and where rigid cervical dilation or local anesthesia was used. The distribution of easy, neutral, or difficult insertions will be summarized by insertion attempt.

Summaries will also be presented for other inserter-related outcomes, such as the number and percentage of subjects where insertion failure occurred, difficulty of insertion, use of cervical dilation, perforation, expulsion, and insertion-related bleeding and cramping.

Some subjects will meet the protocol defined IUS insertion failure, which is when, after advancing through the external cervical os by the inserter, completion of IUS insertion is not achieved. However, some of these insertion failures are unrelated to the study IUS or inserter and such cases will not be analyzed as insertion failures. Examples of such situations include, but are not limited to:

- withdrawal of consent after enrollment and before IUS placement
- cervix could not be visualized
- inserter became contaminated
- subject could not tolerate sounding
- uterus could not be sounded
- uterus sounded to < 5.5 cm
- enrolled but determined not to be eligible before IUS placement

Subjects who had a failed first insertion but never came back for a second attempt are considered to be a failed insertion and not a discontinuation due to withdrawal of consent or lost to follow-up.

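### The SAP starts the Safety population and TEAE window at an insertion attempt, the protocol at the insertion procedure; by protocol 6.6, women stopped before an attempt are missing from the AE tables

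*SAP*

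**What the plan says.** The SAP bases the Safety population on the attempt: "The Safety population will include all subjects enrolled who underwent an IUS insertion attempt, regardless of outcome" (section 6, and to the same effect in its Definitions). Its TEAE definition also starts at the attempt. SAP 11.1 restricts every AE summary to TEAEs, section 11 runs all safety analyses on the Safety population, and 11.1 uses that population as the denominator. SAP section 1 gives the SAP precedence where its analysis differs from the protocol.

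The protocol's Safety population (9.2) is worded differently: "All subjects enrolled who underwent the IUS insertion procedure, regardless of outcome". On enrollment, protocol 4.1 says: "Study entry (enrollment) is defined as the initiation of a study IUS insertion procedure". Protocol 7.13 counts as an AE: "Any untoward event that occurs from the beginning of the IUS insertion procedure until completion of insertion".

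Protocol 6.6 separates the two terms. The general insertion process starts when the kit is opened with intent to insert. An attempt starts only when the inserter goes through the external os. If the process stops earlier, "in such circumstances, an IUS insertion attempt has not occurred". Failure to sound the uterus, and intolerance before the device reaches the os, are among its examples.

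**The concern.** Sounding is deferred to Visit 5: protocol 6.7.2.4 excepts it from the screening pelvic exam, so inclusion criterion 8 (sound depth of at least 5.5 cm) is tested once insertion is under way. Appendix G allows cervical anesthesia and rigid dilators so that the sound can pass. These steps carry risk of their own. Of cervical anesthesia, protocol 7.1.16 says: "Rarely, a seizure or death can occur".

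A harm at this stage that is bad enough to end the procedure is the kind of event that can leave a woman without an attempt. If the Safety population and TEAE window both wait for the attempt, that event is collected but not tabulated. Safety is a secondary objective, and the summarized insertion profile would lack events that stopped insertion early. The count of enrolled women would also depend on the definition used.

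**Working it through.** The documents give no figure on this point to reproduce. The check is a comparison of definitions, followed by an illustration.

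**Test case.** A woman at Visit 5 has the kit opened and cervical anesthesia given. She has an AE, the uterus cannot be sounded, and no later attempt is made.

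| Text | Trigger | Her status |
|---|---|---|
| Protocol 4.1 | procedure initiated | enrolled |
| Protocol 9.2, read with 4.1 | procedure undergone | in Safety |
| Protocol 7.13 | start of procedure | AE recorded |
| Protocol 6.6 | inserter through the os | no attempt |
| Protocol 6.8 | attempt | not enrolled |
| Protocol 7.17.3, read with 6.8 | consented, not enrolled | screen failure |
| SAP 6 and Definitions, read with 6.6 | attempt | outside Safety |
| SAP 11.1, read with 6.6 | during or after attempted insertion | AE not a TEAE |
| Protocol 6.8.2 | includes sounding below 5.5 cm, then refers to AEs related to the attempt(s) | treated as if an attempt occurred |
| Protocol Appendix G | cannot be instrumented, or sounds below 5.5 cm | insertion failure |
| SAP 11.5 | sounding problems listed as examples of protocol-defined failures | failure, but not analyzed as one |

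Protocol 6.8 reads: "An IUS insertion attempt enrolls the subject into the Treatment Phase". SAP 11.5 restates the 6.6 definition of failure (inserter already past the os) and then gives examples that precede that point, such as "uterus sounded to < 5.5 cm". By 6.6 these are stops before an attempt. By Appendix G they are insertion failures.

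**Does another SAP rule bring her back?** SAP 11.1 counts an AE of undetermined status as treatment-emergent. That settles the event, not the population: if she is outside Safety, her events are not tabulated. The date rules in SAP 5.3.4 refer to the insertion attempt date, which she does not have.

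**Who is affected.** Women who never reach an attempt, and events from an aborted session on an earlier day than a later attempt. Events on the same date as an attempt would probably still count.

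**Illustration (counts assumed; the documents give none).** Let k of 100 women stop before an attempt, each with one AE of a given type, and let a women among the rest have that AE.

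- Table under SAP 6 read with 6.6: a / (100 − k)
- Table under protocol 4.1 and 9.2: (a + k) / 100

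| k | a | SAP, strict reading | Protocol population |
|---|---|---|---|
| 1 | 0 | 0/99 = 0% | 1/100 = 1% |
| 2 | 0 | 0/98 = 0% | 2/100 = 2% |
| 5 | 0 | 0/95 = 0% | 5/100 = 5% |
| 1 | 5 | 5/99 = 5.05% | 6/100 = 6% |
| 5 | 5 | 5/95 = 5.26% | 10/100 = 10% |

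These are worst cases for a given k, since every stopped woman is assumed to have the event.

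**The case against.** A reader might infer that the SAP plainly departs from the protocol and drops harmed women. The documents do not support that much, for three reasons.

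- The SAP never defines an attempt. The os-based meaning is imported from protocol 6.6.
- Protocol 6.8 enrolls at the attempt. Since 9.2 covers enrolled women only, 9.2 read with 6.8 gives the same set as SAP 6. Part of the conflict is therefore inside the protocol.
- Protocol 6.8.2, Appendix G and SAP 11.5 treat failed sounding loosely as an attempt or an insertion failure. On that usage the woman stays in the Safety population. SAP 11.5 also declines to analyze these cases as insertion failures, which is the result 6.6 requires.

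The group is also likely to be small. Exclusion 7 removes women whose uterus cannot be appropriately instrumented, and a woman whose screening biopsy cannot be obtained is a screen failure (a documented biopsy within 6 months may stand in). SAEs are reportable from screening and deaths from consent. SAP 5.1 lists individual data by subject, and 7.1 summarizes disposition for all subjects. The anesthesia warning is general risk language, not a rate.

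All of this stands, and it limits the claim. It does not remove it: the one explicit definition in either document leaves her out, and a looser reading keeps her in. Two programmers could produce different Safety populations from the same text.

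**Conclusion.** The inconsistency is established. Under protocol 6.6, women stopped before an attempt drop out of the AE summaries even though their events must be recorded. That they will be dropped is not established, because other passages point the other way.

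The number affected cannot be estimated from the documents and is probably small. At an assumed 100 women, one omitted serious event would move a reported rate from 1% to 0%. The efficacy analyses are untouched, since the ITT and MITT populations and their subsets all require successful insertion. A reader might also infer that such harms go unreported, or that the whole safety profile is materially biased. Neither follows: reporting and listings remain, and only the summary tables and enrollment counts are at risk. The point deserves correction because it is cheap to fix and concerns events that end a procedure.

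**What to change.** In SAP Definitions, 6 and 11.1, define the Safety population as all women in whom the IUS insertion procedure was started, and start the TEAE window at the same point. State that start point explicitly so that it covers anesthesia, dilation and sounding done for insertion. Kit opening, where 6.6 begins the process, may come after some of these steps, so changing *attempt* to *procedure* alone would only move the ambiguity.

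Reconcile the enrollment and failure wording in protocol 4.1, 6.6, 6.8, 6.8.2, 7.17.3 and Appendix G, and in SAP 11.5. Keep women with an attempt as the denominator for the insertion-failure rate, and report procedures stopped before an attempt as a separate category.

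The cost is wording in both documents. A few women without IUS exposure enter the Safety N and slightly dilute rates of later events: with 5 such women, 5/95 = 5.26% becomes 5/100 = 5.00%. Women who fail inclusion 8 at sounding would count as enrolled, and so as major eligibility deviations under SAP 7.2.
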